6.1.2 Phase 0 Dose Limiting Toxicity (DLT) and Maximum Tolerated Dose (MTD)

Dose escalation will proceed according to the following scheme for Phase 0:

Table 8 Phase 0 Dose Escalation Schedule - DLT and MTD

Number of Patients with DLT at a Given Dose Level	Escalation Decision Rule

Initial Version date: 10/16/2018

Revision date: 03/11/2019, 5/07/2019, 09/26/2019, 03/17/2020, 08/26/2024

0 out of 3	Enter 3 patients at the next dose level.
≥ 2	Dose escalation will be stopped. This dose level will be declared the maximally administered dose (highest dose administered). Three (3) additional patients will be entered at the next lowest dose level if only 3 patients were treated previously at that dose.
1 out of 3	Enter at least 3 more patients at this dose level. 
 • If 0 of these 3 patients experience DLT, proceed to the next dose level. • If 1 or more of this group suffer DLT, then dose escalation is stopped, and this dose is declared the maximally administered dose. Three (3) additional patients will be entered at the next lowest dose level if only 3 patients were treated previously at that dose and the lower dose level demonstrated positive PK/PD results (OBD).
≤ 1 out of 6 at highest dose level below the maximally administered dose	This is generally the recommended phase 2 dose (RP2D). If Dose Level 3 is reached, ≤ 1 out of 6 have experienced DLTs and the dose level has demonstrated positive PK/PD results, the time cohort will be expanded.

If one patient develops a DLT out of three, then the cohort will be expanded to include a total of 6 patients. If greater than or equal to two patients develop DLT, then that dose level will be considered the maximum administered dose (MAD) and further dose escalation will be terminated. A total of 6 patients will be treated at the next lower dose. The maximum tolerated dose (MTD) will be the dose at which no more than 1 patient develops DLT when at least 6 patients have been treated.

At the time of dose escalation, a written report will be submitted to the DSMB Chair (or qualified alternate) describing the cohorts, dose levels, adverse events, safety reports and any DLTs observed. The DSMB Chair will review the report and provide a written authorization to proceed or request more information within 2 business days. Approval for the dose escalation must be obtained prior to implementation.

6.1.2.1 Optimal Biological Dose (OBD)

If positive tumor PK and PD effects are observed in patients treated at a specific dose, but no DLT is observed, dose escalation will continue as planned in order to demonstrate whether an increase in biological effect can be observed with increasing dosage or if such effect is maximized (ie, the OBD is attained). If the OBD has been achieved with <2 DLTs out of 6 patients, the OBD cohort will be expanded to an additional 8 patients to assure safety and to evaluate time course of PK and PD effects at 2 time cohorts (i.e., 2 ± 1 h and 24 ± 1 h), with 4 patients in each time cohorts, following the administration of the final dose on Day 5.

6.1.3 Dose Limiting Toxicity for Phase 0 or Phase 2

Dose limiting toxicity (DLT) will be defined as adverse event(s) which is/are attributable to the study treatment and unrelated to disease, disease progression, inter-current illness, or concomitant medications during the first 5 days in Phase 0 or in the first cycle (28 days) of Phase 2. The

maximum tolerated dose of ribociclib+everolimus will be that dose at which fewer than one-third of patients experience a dose limiting toxicity within each Phase. If multiple toxicities are seen, the presence of dose limiting toxicity should be based on the most severe toxicity experienced.

Table 9 DLT Criteria

TOXICITY	DLT CRITERIA
Hematology	CTCAE grade 4 neutropenia for more than 7 consecutive days CTCAE grade 4 thrombocytopenia CTCAE grade 3 thrombocytopenia with bleeding Grade 4 granulocytopenia lasting ≥ 5 days without hematopoietic growth factor support Febrile neutropenia (decrease in neutrophils associated with fever ≥ 38.5°C, ANC < 1.0 x 10 ⁹ /L)
Gastro-intestinal	≥ CTCAE grade 3 vomiting or nausea ≥ 48 hrs despite optimal anti-emetic therapy ≥ CTCAE grade 3 diarrhea ≥ 48 hrs despite optimal anti-diarrhea treatment
Hepato-biliary	CTCAE grade 2 bilirubin for more than 7 consecutive days ≥ CTCAE grade 3 total bilirubin ≥ CTCAE grade 2 ALT with a ≥ grade 2 bilirubin elevation of any duration in the absence of liver metastases ≥ CTCAE grade 3 ALT for more than 4 consecutive days CTCAE grade 4 ALT or AST CTCAE grade 4 serum alkaline phosphatase > 7 consecutive days
Cardiac	Cardiac toxicity ≥ CTCAE grade 3 Clinical signs of cardiac disease, such as unstable angina or myocardial infarction, or Troponin ≥ CTCAE grade 3
ECG QT Interval	QTcF interval ≥ 501 ms on at least two separate ECGs
Renal	≥ CTCAE grade ≥ 3 serum creatinine
Stomatitis	CTCAE Grade 4
Non-infectious pneumonitis	CTCAE Grade 4
Metabolic events (hyperglycemia, dyslipidemia)	CTCAE Grade 4
Non-hematologic events	Inability to receive the subsequent planned dose due to toxicity Inability to begin the next cycle of treatment (at full dose) within 2 weeks of the scheduled dose due to unresolved toxicity Grade ≥ 2 non-hematological toxicity that persists beyond the first 42 days that in the judgment of the Principal Investigator is dose-limiting Certain Grade 2 toxicity (e.g. renal neurological, cardiovascular, gastrointestinal) which in the judgment of the Principal Investigator is dose-limiting ≥ CTCAE grade 3, except for the exclusions noted below:
Exceptions to DLT criteria	< 5 days of CTCAE grade 3 fatigue Untreated nausea or vomiting, or alopecia Grade 3 laboratory abnormalities that are responsive to oral supplementation or deemed by the investigator to be clinically insignificant
CTCAE version 4.03 will be used for all grading. Optimal therapy for vomiting or diarrhea will be based on institutional guidelines, with consideration of the prohibited medications listed in this protocol.	

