6.1.1 Phase 0 & 2 Dose Escalation Schedule

Table 7 Dose Escalation Schedule

Dose Level	Phase 0 Dose of Study Drug ^a	Minimum Number of Patients	Phase 2 Dose of Study Drug ^a
0	ribociclib 400mg and everolimus 2.5mg	6	ribociclib 400mg and everolimus 2.5mg
1	ribociclib 600mg and everolimus 2.5mg	3	ribociclib 600mg and everolimus 2.5mg

Initial Version date: 10/16/2018

Revision date: 03/11/2019, 5/07/2019, 09/26/2019, 03/17/2020, 08/26/2024

Dose Level	Phase 0 Dose of Study Drug ^a	Minimum Number of Patients	Phase 2 Dose of Study Drug ^a
2	ribociclib 600mg and everolimus 5mg	3	ribociclib 600mg and everolimus 5mg
3	ribociclib 600mg and everolimus 10mg ^b	3	ribociclib 600mg and everolimus 10mg ^c
4	ribociclib 600mg, qd and everolimus 50mg once ^d	3	ribociclib 600mg daily and everolimus 50mg once weekly ^e
5	ribociclib 600mg, qd and everolimus 60mg once ^d	3	Cycle 1: ribociclib 600mg, qd and everolimus 50mg once weekly ^e Cycle 2+: 600 mg, qd and everolimus 60mg once weekly ^f
6	ribociclib 600mg, qd and everolimus 70mg once ^d	3	Cycle 1: ribociclib 600mg, qd and everolimus 50mg once weekly ^e Cycle 2: 600 mg, qd and everolimus 60mg once weekly ^f Cycle 3+: 600 mg, qd and everolimus 60mg once weekly ^f

- a. The Phase 0 dose given to the patient will be the RP2D. If more than one DLT is observed in 6 patients in Phase 2, the regimen at that given level will be considered as the maximal administered dose and the next lower dose level will be the MTD/RP2D for subsequent patients enrolled into Phase 2
- b. In Phase 0, the everolimus dose will be given in one dose (10mg, qd).
- c. In Phase 2, dose will be given in two doses (5mg, bid)
- d. In Phase 0, the everolimus dose will be given in one dose on Day 5 only; ribociclib dose will be given daily for 5 days.
- e. In Phase 2, everolimus dose will be given once weekly on Days 1, 8, 15, 22 of each cycle with ribociclib administered daily for 21 consecutive days and 1 rest week.
- f. If the dose is well tolerated in Cycle 1, the dose may be escalated based on investigator discretion.

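### At Levels 4–6 the only Phase 0 everolimus dose falls on the last day of the DLT window, and no scored Phase 2 window contains 60 or 70 mg weekly, so an MTD or RP2D at those doses would not rest on scored data

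*Combined protocol and SAP*

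**What the plan says.** Section 6.1.3 counts DLTs "during the first 5 days in Phase 0 or in the first cycle (28 days) of Phase 2". Table 7 (Section 6.1.1) holds ribociclib at 600 mg across Levels 4–6 and changes only everolimus: 50, 60 and 70 mg. Its footnote d reads: "In Phase 0, the everolimus dose will be given in one dose on Day 5 only". Section 4.1.1 puts escalation patients at Levels 2 and above in time Cohort 2, where craniotomy follows the last dose by 7 to 9 hours.

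For Phase 2, Table 7 gives 50 mg weekly at Level 4. Levels 5 and 6 both begin with "Cycle 1: ribociclib 600mg, qd and everolimus 50mg once weekly". Footnote e adds that the "everolimus dose will be given once weekly on Days 1, 8, 15, 22 of each cycle". For doses above 50 mg, footnote f says: "If the dose is well tolerated in Cycle 1, the dose may be escalated based on investigator discretion".

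On the declared dose, footnote a says "The Phase 0 dose given to the patient will be the RP2D". It adds a step-down rule: "If more than one DLT is observed in 6 patients in Phase 2, the regimen at that given level will be considered" too high, and the next lower level becomes the MTD/RP2D. Section 6.1.2 sets the MTD as a dose with at most one DLT once six or more patients have been treated. Section 4.1.2 bases Phase 0 escalation on the Phase 0 DLT rules alone, unless the DSMB decides otherwise.

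**The concern.** MTD is a primary endpoint and RP2D a secondary one (Section 3). An escalation rule is informative only if its window can see toxicity from the drug being escalated. A 5-day window suits Levels 0–3, where everolimus is taken daily from Day 1. It does not suit a single dose on Day 5.

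Several Table 9 criteria need time: at least 48 hours, more than 4 days, or more than 7 days. None of these can be completed between the Day 5 dose and the end of Day 5. Table 13 also lets the pre-surgical labs and ECG be done on Day 4, before any everolimus at these levels. The next labs it schedules are at the post-operative visit.

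Delayed toxicity is a realistic possibility here. Section 6.1.5 expects ribociclib to raise everolimus exposure and projects a 3.5-fold increase with ribociclib 200 mg; these levels use 600 mg.

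Followed as written, the rule can clear 60 or 70 mg with almost no scored exposure to it, and can open the next level before post-operative data exist. A weekly dose that was never scored could then be carried forward as the RP2D.

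**Working it through.** **1. The plan's own threshold.** Section 3 sets the MTD limit at 17%. Since 1/6 = 16.7% and 2/6 = 33.3%, the count in Section 6.1.2 (at most 1 of 6) matches it. The question is which events enter the count.

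**2. Phase 0.** The window is Days 1–5 (6.1.3) and the dose is on Day 5 (Table 7, footnote d). Full scored days after the dose: 5 − 5 = 0. At most 24 of 120 window hours (20%) follow the dose, and in Cohort 2 they include the craniotomy.

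**3. Phase 2.** The window is Cycle 1, with weekly doses on Days 1, 8, 15 and 22. Everolimus doses given at the level's own dose inside a scored window:

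| Level | Phase 0 | Phase 2, Cycle 1 |
|---|---|---|
| 4 (50 mg) | 1 | 4 |
| 5 (60 mg) | 1 | 0 |
| 6 (70 mg) | 1 | 0 |

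Scored Cycle 1 everolimus is 4 × 50 = 200 mg at every level. Four weeks at 60 mg would be 240 mg (20% more), and at 70 mg 280 mg (40% more).

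**4. Does Table 9 close the gap?** Three of its lines look past the window. Two concern inability to take the next planned dose, or to start the next cycle within 2 weeks; at Levels 4–6 no Phase 0 dose follows Day 5. The third concerns toxicity lasting past 42 days, with no stated starting point. Counted from Phase 2 Day 1, Cycle 2 doses fall on Days 29, 36, 43 and 50, so only two 60 mg doses precede Day 42. Cycle 3 starts on Day 57. None of the three defines an assessment at 60 or 70 mg.

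**5. Illustration only.** Let p be the true DLT rate and f the share of DLTs that appear on the dosing day. The documents give neither, so both are assumed. With r = p × f:

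- Table 8 pass = (1−r)³ + 3r(1−r)² × (1−r)³
- At most 1 of 6 = (1−r)⁶ + 6r(1−r)⁵

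| p | f | r | Table 8 pass | At most 1 of 6 |
|---|---|---|---|---|
| 0.40 | 1 | 0.40 | 31% | 23% |
| 0.40 | 0.5 | 0.20 | 71% | 66% |
| 0.40 | 0.25 | 0.10 | 91% | 89% |
| 0.30 | 1 | 0.30 | 49% | 42% |
| 0.30 | 0.5 | 0.15 | 81% | 78% |
| 0.30 | 0.25 | 0.075 | 94% | 93% |

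The last column applies only if six patients are treated. DSMB discretion is not modelled.

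**6. Phase 2 numbers.** Section 9.7.1 assumes at most 50% of Phase 0 patients continue. A level of 3–6 patients gives 1.5–3, and a level expanded to 14 gives 7.

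**The case against.** **The choice is deliberate and gated.** Section 4.1.2 acknowledges that DLT windows are usually 28 days and explains the shorter one by the 5-day treatment. Adverse events are collected to 30 days after the last dose. There is a post-operative visit and a 30-day call, and the DSMB Chair must approve each escalation on a report that includes adverse events. All of this stands, so a reader who inferred that patients go unwatched after Day 5 would be wrong. But none of it requires post-dose data to exist before the decision, and none puts later events into the MTD count. The DSMB charter is a separate document and may set a minimum follow-up; that cannot be seen here.

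**The window may be softer than it looks.** Section 6.1.3 could be read as covering any later event caused by treatment given in those days, and some Table 9 criteria outlast Day 5. On that reading the window has no closing day, and the same change is needed.

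**Table 8 does not name 70 mg.** One might infer that its last row could make 60 or 70 mg the RP2D. That row covers only a level below the maximally administered dose. It can never name Level 6, and it can name Level 5 only if Level 6 is declared the maximally administered dose. This stands. The remaining routes are footnote a and the MTD rule in Section 6.1.2. Footnote a may mainly say which dose a continuing patient takes, but it does use the term RP2D.

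**The percentages are not operating characteristics.** This also stands. Under Table 8, 0 of 3 moves on with three patients. The path of 1 of 3 and then 0 of 3 has probability 3r(1−r)²(1−r)³, which is 9%, 20% and 18% at r = 0.4, 0.2 and 0.1. Nor do the figures compare the current rule with the proposed one, which would itself miss DLTs arising after the post-operative visit.

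**Conclusion.** The point holds, and it rests on counting doses against scored days, with no assumed rates. At Levels 4–6 there are no full scored days after the only Phase 0 everolimus dose. At Levels 5 and 6 no scored Phase 2 dose is at the level's own strength. An MTD or RP2D at 60 or 70 mg weekly would therefore be unsupported by the scored data. Level 4 is different: its 50 mg weekly regimen does have a matching scored cycle, though its Phase 0 escalation decision shares the same-day limit.

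The percentages show only how a same-day window could weaken the rule if DLTs were delayed. They do not show that 60 or 70 mg is unsafe, and the documents give no DLT rate at these doses.

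A reader might also infer from Table 7, which prints 60 mg for Level 6 from Cycle 3 onward, that 70 mg weekly is never intended. Section 2.3 and Table 10 point to 70 mg, so this looks like a typing error. The conclusion does not depend on it, because Cycle 3 is unscored either way.

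**What to change.** **(1) Phase 0, Section 6.1.3, Levels 4 and above.** Run the DLT period from first dose to the existing post-operative visit 7–14 days after surgery, or to the start of Phase 2 if earlier. For Cohort 2, with surgery on Day 5, the visit falls on Days 12–19. Count events with onset in that period and follow them through for criteria that need a duration. Keep the Section 8.1.1 rule for clearly surgical events. Require the period to be complete before the Table 8 decision and the DSMB report.

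**(2) Phase 2.** State that 60 or 70 mg weekly will not be declared the MTD or RP2D on Cycle 1 data at 50 mg. Report tolerability over the first 28 days at each higher dose descriptively, unless that dose has been scored in as many patients as the rule requires. Use the scheduled visits. From Cycle 3 Table 13 has hematology and chemistry on Day 1 only, so the next cycle's Day 1 labs close the period.

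**Cost.** Fix (1) needs no new visit. It adds a 7–14 day wait per decision: 3 × 7–14 = 21–42 days if no level expands, and 6 × 7–14 = 42–84 days if all three expand to six, against accrual planned within 12 months (Section 9.7.2). A window that runs past craniotomy brings some confounding, which the attribution rule resolves only for clearly surgical events. With 1.5–3 Phase 2 patients expected at an unexpanded level, fix (2) probably means no RP2D declaration at 60 or 70 mg weekly unless a level is expanded.

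**Separate minor corrections.** Align the three Table 9 lines with the Section 6.1.3 windows, define where the 42 days start, and check the Level 6 entry for Cycle 3 onward.

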4.1 Description of protocol design

4.1.1 Phase 0

In the proposed trial, patients will be administered ribociclib+everolimus prior to surgical resection of their tumor. Recurrent GBM patients will be randomized into one of the three time-interval cohorts for the first two dose levels.

In the lead-in dose escalation study, the first six subjects (lead-in) will receive ribociclib 400 mg and everolimus 2.5 mg orally-administered in 5 daily doses with the last dose. If one or less patient experiences DLT among the 6 patients, this regimen with ribociclib 400 mg and everolimus 2.5mg will be considered safe and we will continue with the dose escalation phase of the study up to Level 6.

Four dose escalation levels:

Level 0: ribociclib 400mg and everolimus 2.5

Level 1: ribociclib 600mg and everolimus 2.5mg

Level 2: ribociclib 600mg and everolimus 5mg

Level 3: ribociclib 600mg and everolimus 10mg

Level 4: ribociclib 600mg daily for 5 days and everolimus 50mg given once on Day 5.

Level 5: ribociclib 600mg daily for 5 days and everolimus 60mg given once on Day 5.

Level 6: ribociclib 600mg daily for 5 days and everolimus 70mg given once on Day 5.

Three to fourteen (3-14) patients will be enrolled into each level to observe AEs and DLTs. Detailed DLTs definition will be summarized in [Table 9](#).

All patients will receive ribociclib and everolimus orally-administered in 5 daily doses.

Cohort 1: last ribociclib+everolimus dose 1 to 3 hours prior to craniotomy for tumor resection (n=8 patients)

Cohort 2: last ribociclib+everolimus dose 7 to 9 hours prior to craniotomy for tumor resection (n=8 patients)

Cohort 3: last ribociclib+everolimus dose 23 to 25 hours prior to craniotomy for tumor resection (n=8 patients)

In Dose Level 0 three to six patients will be enrolled into the time interval cohorts, sequentially whenever possible (e.g. cohort 1, cohort 2, cohort 3, cohort 1...), with at least 1 patient in each of the time intervals.

In Dose Level 1

Three to six patients will be enrolled into the time interval cohorts, sequentially whenever possible (e.g. cohort 1, cohort 2, cohort 3, cohort 1...), with at least one patient in time cohort 1 and two patients in cohort 2. If there are positive PK/PD results at the Maximum Tolerated Dose (MTD) or Optimal Biological Dose (OBD) dose level, the dose level will be expanded to 8 additional patients with 4 patients in each time cohort 1 and 3 (Sections [6.1.2](#) and [6.1.2.1](#)).

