In Dose Levels 2+, three to six patients will be enrolled into cohort 2. If there are positive PK/PD results at the Maximum Tolerated Dose (MTD) or Optimal Biological Dose (OBD) dose level, the dose level will be expanded to 8 additional patients with 4 patients in each time cohort 1 and 3 (Sections [6.1.2](#) and [6.1.2.1](#)).

Dose Level	Time Interval	N=	Dose Expansion Cohort N=	Time Cohort Expansion N=
Level 0	Cohort 1	2	N/A	N/A
	Cohort 2	2		
	Cohort 3	2		
Level 1	Cohort 1	1	0	4
	Cohort 2	2	3	0
	Cohort 3	0	0	4
Level 2	Cohort 1	0	0	4
	Cohort 2	3	3	0
	Cohort 3	0	0	4
Level 3	Cohort 1	0	0	4
	Cohort 2	3	3	0
	Cohort 3	0	0	4
Level 4 - 6	Cohort 1	0	0	4
	Cohort 2	3	3	0
	Cohort 3	0	0	4

To assess the PK and PD endpoints listed above, blood, CSF and brain tumor tissue will be collected intraoperatively (enhancing and non-enhancing tumor tissue will be collected and analyzed separately).

Additionally, blood samples will be obtained on Day 4 in Dose Levels 1-3 (the day before the surgery for Cohorts 1 & 2; 2 days before surgery for Cohort 3) at pre-dosing (trough level), 0.5, 1, 2, 4, 7, and 24 hours post dose. (Note: 24 h sample is the pre-dosing (trough level) blood sample on Day 5).

Dose Level 4+ only: PK blood sampling will occur on Day 5: pre, 0.5, 1, 2, 4, 6, 8 and 24 hours post-dose (Note: 24 h sample is the pre-dosing (trough level) blood sample on Day 6).

Dose Levels 0-3:

[figure not shown]
PHASE 0 STUDY COHORT 1										
DAY 4 PRE- DOSE	Time 0	30 min	1 hour	2 hours	3 hours	4 hours	7 hours	24 hours ± 1 h	POSTOP- Phase 2	
Blood			Blood	Blood	Blood		Blood	Blood	Blood	
DAY 5 PRE- DOSE	Ribociclib + everolimus								Ribociclib + everolimus	
Blood			Blood* CSF* Tumor*							

PHASE 0 STUDY COHORT 2										
DAY 4 PRE- DOSE	Time 0	30 min	1 hour	2 hours	4 hours	7 Hours	8-9 Hours	24 hours ± 1 h	POSTOP- Phase 2	
Blood			Blood	Blood	Blood	Blood	Blood		Blood	
DAY 5 PRE- DOSE	Ribociclib + everolimus								Ribociclib + everolimus	
Blood			Blood* CSF* Tumor*							

PHASE 0 STUDY COHORT 3										
DAY 4 PRE- DOSE	Time 0	30 min	1 hour	2 hours	4 hours	7 Hours	23 -25 hours	POSTOP- Phase 2		
Blood	Ribociclib + everolimus		Blood	Blood	Blood	Blood	Blood	Blood	Ribociclib + everolimus	

Initial Version date: 10/16/2018

Revision date: 03/11/2019, 5/07/2019, 09/26/2019, 03/17/2020, 08/26/2024

[figure not shown]

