4.1.2 Phase 2 Dose expansion

Patients with tumors demonstrating favorable PK and PD will proceed to Phase 2 Dose Expansion. In Dose Levels 1-3, patients will continue treatment with the same treatment level as given in Phase 0, patients should take the treatment continuously in 28d cycles with 3 weeks on / 1 week off after surgery. In Dose Level 4+, patients should take everolimus in one dose weekly; ribociclib will be taken for 21 consecutive days followed by 1 rest week. The dose will be per Table 7. If more than one DLT is observed in 6 patients in the Phase 2 dose expansion, the enrollment will be stopped and the previous lower dose level will be considered the RP2D and will be given for the remaining patients enrolled. If more than one DLT is occurred with the Level 0, the study will be stopped due to toxicity. Typically DLTs are defined by 1 cycle of treatment, which is 28 days. Since Phase 0 treatment is given for only 5 days, Phase 0 dose escalation will only be determined by Phase 0 DLT rules unless determined otherwise by the DSMB. Patients will be treated until unacceptable toxicity is observed, or until disease progression as assessed by radiographic or clinical metrics. Preliminary rates of progression-free survival in patients with high-grade gliomas treated with ribociclib+everolimus will be measured through radiographic and clinical response metrics, specifically Response Assessment in Neuro-Oncology (RANO) criteria and investigator discretion. Phase 2 participants will return to the clinic to monitor safety per the schedule of events until treatment is ended and will then be contacted approximately every 3 months by letter or phone for collection of survival data. The start of follow up for long-term survival begins following completion of the Day 30 safety follow up call.. All Phase 0/2 participants will be followed for survival for up to 5 years.

Common Toxicity Criteria Adverse Event (CTC AE 4.03) will be utilized to review ribociclib+everolimus treatment effects in patients with brain tumors.

Trough steady-state blood samples will be obtained on days 1, 8, 15, and 22 of cycles 1 and 2 prior to the administration of ribociclib+everolimus on that day. Note: ribociclib+everolimus will be administered in the clinics on the clinic visit days to ensure the collection of trough level samples.

PHASE 2 STUDY				
	Cycle 1 (28 d)	Cycle 2 (28d)	Subsequent cycles (28d)	End of study
Day of cycle	D1, D8, D15, D22	D1, D8, D15, D22	N/A	N/A

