2	Screening assessment may be completed at Day 1 predose, if completed at screening, does not need to be repeated at Day 1 pre-dose except for ECG and ECOG. Results must be available to confirm eligibility prior to dosing.											
3	Estimated glomerular filtration rate (eGFR)											
4	ECG Day 1 Pre-dose, Day 1: 2-4 hrs post-dose, and pre-surgical assessment (can be completed on Day 4 or Day 5 (Cohort 1&2) / Day 6 (Cohort 3)).											
5	ECG Pre-dose and 2-4 hours post dose on C1D15, C2D15, C3D1, C6D1; C9D1; and every 3 rd cycle...											
6	ECG Pre-dose C2D1, C4D1, C5D1; C7D1, C8D1, C10D1, C11D1; and every 1st and 2nd cycle...											
7	Performed at pre-surgical assessment as per SOC on Day 4 (can be completed on Day 5 (Cohort 1&2) or Day 6 (Cohort 3)).											
8	Lipid panel performed every 4th cycle D1											
9	Study drugs are administered in the clinics on D1, D4 and D5. Patients may take medications at home on D2 and D3											
10	Trough blood sample is collected prior to the drug administration on that day. Study drugs are administered in the clinics on the clinic visit days 1, 8, 15, 22.											
11	Blood samples will be obtained on Day 4 (the day before the surgery for Cohorts 1 & 2; 2 days before surgery for Cohort 3) at pre-dosing (trough level), 0.5, 1, 2, 4, 7 hours post dose (\pm 5 min window for 0.5hr and 1hr; \pm 15min window for 2, 4, 7hr samples). A pre-dosing (trough level) blood sample will also be obtained on Day 5 and a sample will be collected intra-operatively. In Dose Level 4+ only, PK blood sampling will occur at the same timepoints (pre, 0.5, 1, 2, 4, 6, 8 and 24) but will be obtained on Day 5 (the day of surgery); the 24 hour sample will be obtained on Day 6.											
12	Only Patients that have a recurrence and undergo an additional surgery for tumor resection											
13	The start of follow up for long-term survival begins following completion of the Day 30 safety follow up call. Subjects will continue to be followed until death or withdrawal of consent for the collection and reporting of data or lost to follow-up for up to 5 years. Public records may be used to collect survival data, i.e., obituary notices and public database searches for survival information.											

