7.1.1.11.1 Day 1 Enrollment

The following assessments will be performed on Day 1:

- Review of surgical and medical procedures
- ECOG
- 12-lead ECG
- Collection of AEs and Concomitant medication(s)
- Screening assessments not previously collected as noted in section [7.1.1.9](#)
- Day 1 pre-dose PK sample
- Day 1 pre-dose biomarker blood sample
- Confirm eligibility prior to study drug administration
- In clinic/hospital study drug administration
- Provide the patient the following for home dosing on Days 2 and 3
 - Instructions for study medication
 - Dosing Diary
 - Symptom Diary
 - Study drug

7.1.1.11.2 Day 2 and 3

Phase 0 patients will record study drug administration in the Dosing Diary and record symptoms in the Symptom Diary.

7.1.1.11.3 Day 4

The following assessments will be performed on Day 4:

- Review of medical and surgical procedures
- Collection of AEs and Concomitant medication(s)
- Review of home dosing diary and symptom diary

- 12-lead ECG
- Trough PK Sample (Dose Levels 0-3)
- Laboratory testing (may also be performed as a pre-surgical assessment on Day 5 or Day 6):
 - Chemistry, (comprehensive metabolic panel, magnesium, phosphorus)
 - Hematology (CBC w/differential)
 - Coagulation (PT/INR, aPTT)
 - eGFR
- In clinic/hospital study drug administration
- PK blood sampling: 0.5, 1, 2, 4, 7 hours post-dose (Dose Levels 0-3)
 - *In Dose Level 4+ only, PK blood sampling will occur on Day 5 instead of Day 4.*

7.1.1.11.4 **Day 5**

- Review of medical and surgical procedures
- Collection of AEs and Concomitant medication(s)
- 12-Lead ECG (if not collected on Day 4)
- In clinic/hospital study drug administration
- Craniotomy (Day 5 for Cohort 1 & 2; Day 6 for Cohort 3)
 - PK Collection of blood, CSF and tumor
 - Biomarker tumor collection
- Dose Level 1-3: Day 5 trough/24hrs post-dose
- Dose Level 4+ only: PK blood sampling: pre, 0.5, 1, 2, 4, 6, 8 and 24 hours (Day 6) post-dose

7.1.1.11.5 **Follow-up / EOT visit**

Phase 0 patients will have a follow up visit 7-14 days after surgery (routine post-operative visit). All Phase 2 patients should be scheduled for an EOT visit within 7 (± 3) days following discontinuation of study treatment.

The following assessments will be performed at the EOT visit:

- Physical exam
- ECOG performance status
- Weight
- Vital signs
- Laboratory blood collections
 - CMP, magnesium, phosphorus
 - Hematology (CBC w/differential)
 - Urine pregnancy test (if applicable)
- 12-lead ECG

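### At Dose Levels 4-6 no safety laboratory test is required between the only everolimus dose, on Day 5, and the end of the 5-day Phase 0 DLT window

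*Combined protocol and SAP*

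**What the plan says.** Section 6.1.3 limits DLTs to events occurring "during the first 5 days in Phase 0 or in the first cycle (28 days) of Phase 2". Section 4.1.2 makes that short window decisive for escalation: "Phase 0 dose escalation will only be determined by Phase 0 DLT rules unless determined otherwise by the DSMB".

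For Levels 4-6, note d to Table 7 states: "In Phase 0, the everolimus dose will be given in one dose on Day 5 only". Ribociclib 600 mg is given on all five days. Escalation patients at these levels go into one time cohort (Section 4.1.1: "In Dose Levels 2+, three to six patients will be enrolled into cohort 2"), in which surgery is on Day 5, with the "last ribociclib+everolimus dose 7 to 9 hours prior to craniotomy for tumor resection".

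Footnote 7 to Table 13 places hematology, chemistry, eGFR and coagulation as follows: "Performed at pre-surgical assessment as per SOC on Day 4". It allows Day 5 instead for Cohorts 1 and 2, or Day 6 for Cohort 3. The Day 5 visit list in Section 7.1.1.11.4 has no safety laboratory item of its own. The next dated hematology and chemistry are at the post-operative visit (Section 7.1.1.11.5: "Phase 0 patients will have a follow up visit 7-14 days after surgery").

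PK sampling was adapted to the single dose. At Level 4 and above it moves to Day 5, and "the 24 hour sample will be obtained on Day 6" (Table 13, footnote 11).

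Table 9 makes Grade 4 hyperglycemia or dyslipidemia a DLT. Table 13 schedules lipids at screening or Day 1 pre-dose, then on Day 1 of every fourth Phase 2 cycle.

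**The concern.** DLT and MTD are a primary endpoint. At Levels 4-6 the toxicity window closes on the day the drug being escalated is first given, and the default laboratory panel precedes that drug. Laboratory toxicity without symptoms is found only if someone draws blood. Here a site can follow every instruction and have nothing post-everolimus to report to the DSMB Chair when it asks to move from 50 to 60 mg, or from 60 to 70 mg. Any event missed in this way can only lower the DLT count, so the error runs toward escalation.

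The plan gives its own reasons to look. Section 6.1.5 singles out blood counts, liver function tests and QTc for special attention, and expects ribociclib to raise everolimus exposure. Section 1.2.2.3 attributes the more common metabolic effects of the class to lipid and glucose pathways. Section 2.3 takes 70 mg weekly from other combinations as a suggested maximum tolerated dose, so Level 6 is at that limit.

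The rationale for the short window in Section 4.1.2 is that Phase 0 treatment lasts five days. That suits five daily everolimus doses. It does not suit one dose on the fifth day.

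**Working it through.** The plan states no figure to reproduce. The check sets the dosing days, the laboratory days and the DLT windows on one calendar.

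**Everolimus given before the default Day 4 panel** (doses from Table 7)
- Level 3, 10 mg daily: 3 x 10 = 30 mg if drawn pre-dose, or 4 x 10 = 40 mg if post-dose, of 5 x 10 = 50 mg. That is 60-80%.
- Levels 4, 5 and 6: 0 of 50, 60 or 70 mg. That is 0%.

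**Time left in the window after everolimus**
- Dose on Day 5, window closes at the end of Day 5: under 24 hours.
- If the optional pre-surgical draw is used on Day 5 in Cohort 2, surgery follows the last dose by 7-9 hours. That draw is therefore at most 9 hours post-dose, and nothing stops it from being pre-dose.
- Required safety panels after the dose and by the end of Day 5: 0.

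**Next dated blood count and chemistry** (7-14 days after surgery)
- Day 5 surgery: 5 + 7 = Day 12 to 5 + 14 = Day 19, which is 7-14 days after the dose.
- Day 6 surgery (Cohort 3, if a level is expanded): Days 13-20.
- Both fall outside the 5-day window.

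**Does the Phase 2 window cover these doses?** (Table 7; window = Cycle 1)
- Level 4: Cycle 1 is 50 mg weekly, so the level's own dose is covered, for patients who continue.
- Level 5: Cycle 1 is 50 mg, with 60 mg only from Cycle 2.
- Level 6: Cycle 1 is 50 mg, with increases only from Cycle 2.
- So 60 and 70 mg are given inside a DLT window only in Phase 0. Moreover, only patients with positive PK and PD proceed, assumed in Section 9.7.1 to be at most 50%.

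**Patients concerned**
- 3 levels x 3 to 6 patients = 9 to 18 in escalation. Section 6.4.2 describes rotation through all three time cohorts rather than Cohort 2 alone, but the Day 4 default is the same under either reading.

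**Lipids**
- On-treatment panels in Phase 0 Days 1-5: 0. In Phase 2 Cycle 1, Days 1-28: 0.
- If every fourth cycle means Cycle 4 first: 3 x 28 + 1 = Day 85, which is 85 - 28 = 57 days after the window closes.
- If counted from Cycle 1, a Day 1 draw comes at the start of that cycle's dosing, and the next is Cycle 5 Day 1: 4 x 28 + 1 = Day 113.
- Chemistry, which includes glucose, is drawn on Cycle 1 Day 15, so the Phase 2 gap concerns lipids only.

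**The case against.** The strongest reply is that the short window is deliberate and guarded. Section 4.1.2 acknowledges that 28 days is usual, explains the departure, and lets the DSMB decide otherwise. Section 7.2.2 permits testing at any time on clinical judgment and foresees laboratory tests under routine pre- and/or postoperative practice. Section 8.6 extends safety review to the perioperative period under a charter not included here. The DSMB Chair must authorize each escalation. Adverse events are collected for 30 days after the last dose. Repeat dosing in Phase 2 starts at 50 mg even for Levels 5 and 6, after the post-operative labs.

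Much of this stands. A reader might infer that patients go unmonitored after everolimus. The documents do not support that: clinical events are collected continuously, and post-craniotomy bloods may well be drawn. The low Phase 2 starting dose also limits the harm from a wrongly cleared level. But none of these provisions requires a post-dose laboratory result before Level 4, 5 or 6 is cleared, none counts a later result as a Phase 0 DLT, and Section 6.1.2 sets no minimum follow-up before the report goes to the DSMB Chair.

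Other stronger readings also fail:
- **Duration criteria.** A reader might infer that criteria longer than 7 days are unworkable. Table 9 serves both phases, they can be met in Phase 2, and counting by onset is the natural reading.
- **Troponin.** A reader might infer that a test is missing. The criterion shares an entry with clinical signs of cardiac disease and can be read as event-driven.
- **Lipids at Levels 0-3.** This is largely moot, since Section 2.3 describes Levels 4-6 as added after experience at the lower doses.
- **Exposure.** A reader might scale the interaction in Section 2.1 up to 50-70 mg. Those data are steady-state, from a triplet with exemestane, at 2.5 mg everolimus with ribociclib 200-350 mg. They do not establish a multiplier for one large dose with ribociclib 600 mg.

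**Conclusion.** The concern holds for Levels 4-6 and should be fixed by amendment. Zero safety panels are required between the only everolimus dose and the close of the Phase 0 DLT window, under 24 hours remain after that dose, and the next dated panel is 7-14 days after it (Day 5 surgery). For 60 and 70 mg no other DLT window exists. The lipid gap is real but secondary, because only Grade 4 qualifies under the metabolic row and entry criteria already control baseline lipids.

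This rests on reading the first 5 days literally as Days 1-5, and on what the schedule requires rather than what sites may do in practice. The separate DSMB charter could impose more.

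A reader might go on to infer that the MTD will be overstated by some amount. The direction follows, since a missed event can only lower the count. The size does not: the documents give neither the rate of silent laboratory DLTs after one dose nor the share that routine care would catch.

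**What to change.** 1. In Section 6.1.3, for Levels 4-6, run the Phase 0 DLT window through the post-operative visit labs already in Table 13, which come before Phase 2 starts. Do not clear the level until those results are in. This is the essential change, because Day 6 results alone would still fall outside the present window.
2. At Levels 4-6, add a blood count, chemistry and a lipid panel to the existing 24-hour PK draw on Day 6.
3. In Phase 2, add a lipid panel to the existing Cycle 1 Day 15 draw.

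**Cost.** One amendment to Section 6.1.3 and Table 13, and no new visits. A few extra tubes are needed for 9-18 escalation patients, plus one lipid panel per Phase 2 patient. The decisions from Level 4 to 5 and from Level 5 to 6 would each wait about 7-14 days after the last patient's surgery: 2 x 7 = 14 to 2 x 14 = 28 days in all if neither level is expanded. Ascertainment at Levels 4-6 would differ from that at Levels 0-3, which should be stated when DLT rates are reported together. Some abnormalities after craniotomy, and possibly steroids, will be hard to attribute. Section 6.1.3 already excludes events due to intercurrent illness or concomitant medication, so attribution should be recorded case by case.
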